7.3.3 OTHER DATA

The following blood data also will be collected at baseline, 3 months, and at each annual visit:

Complete blood count (CBC): including White Blood Cell Count (WBC), Red Blood Cell Count (RBC), Hemoglobin (Hgb), Hematocrit (HCT), and platelet count (PLT), and plasma free hemoglobin.

Serum creatinine will be collected at baseline only.

Coagulation profile will be collected at baseline, discharge, 3 months, and at the 1, 3, and 5 year follow-up visits.

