9.5 OTHER DATA

The mean and standard deviation of blood data will be calculated and presented.

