10.4 POST-PROCEDURE

10.4.1 POST-PROCEDURE CARE

At the discretion of the investigator, bioprosthetic heart valve recipients should be maintained on anticoagulant therapy (except when contraindicated) during the initial healing stages after implant, approximately 2 to 3 months in accordance with the ACC/AHA 2008 Guidelines for the Management of Patients with Valvular Heart Disease.⁶ Anticoagulants should then be discontinued over a period of 10 days, except in those patients for whom ongoing anticoagulant protection is indicated, i.e. in the absence of sinus rhythm and in patients with a dilated left atrium, calcification of the atrial wall, history of previous atrial thrombus, or any other medical condition requiring anticoagulation therapy. However, the appropriate anticoagulation therapy must be determined by the physician on an individual basis.

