10.4.3 FOLLOW-UP ASSESSMENTS

Post-procedure clinical evaluation will be performed on all enrolled trial subjects at scheduled visits at the trial site. The follow-up windows are listed in **Table 7**.

Table 7: Follow-up Windows

Follow-up Assessment*	Assessment Window
3 months	± 1 month
1 year	± 1 month
2 years	± 3 month
3 years	± 3 month
4 years	± 3 month
5 years	± 3 month

*Follow-up visits are calculated from the implant date.

During each postoperative follow-up visit, the investigator(s) will determine the subject's availability for future follow-up visits. If any subject needs to be seen, at a time other than a regularly scheduled follow-up visit, due to an index device related event, the required data collection would be the same as the 1 year follow-up evaluation.

Table 8 Follow-Up Information at all Post-Discharge Visits (3 months and annually to 5 years)

Clinical/Physical Assessment	Blood Studies	Echocardiography (TTE) ³
Date of Discharge	Blood Draw Date	Years 1, 3, 5:
Physical Assessment	White Blood Cell Count	Date of exam
Cardiac Rhythm (12-lead ECG)	Red Blood Cell Count	SEE ECHO MANUAL
NYHA Classification	Hemoglobin	Years 2, 4:
Quality of Life (EQ-5D & SF12-v2) ¹	Hematocrit	Date of exam
Anti-thromboembolic Therapy (medications)	Platelet Count	Auscultation ⁴
Adverse Events	Plasma Free Hemoglobin	
	Coagulation Profile ²	

¹ Quality of Life (EQ-5D and SF12-v2) will be completed only at the 1-year follow-up visit

² Coagulation profile will be completed only at years 1, 3, and 5

³ Exam to be performed as described in the Echo Manual. Data evaluation performed by a Core Lab.

⁴ TE will be the standard echo assessment for the aortic valve but will only be completed if murmur is heard on auscultation at year 2 and year 4 interval visits.

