3 MONTHS

- 6.01 3 MONTHS - SUBJECT NOT CONTACTED
- 6.02 3 MONTHS - ASSESSMENT NOT DONE WITHIN FOLLOW-UP WINDOW
- 6.03 3 MONTHS - PHYSICAL ASSESSMENT / VITAL SIGNS NOT DONE
- 6.04 3 MONTHS - NYHA NOT DONE
- 6.05 3 MONTHS - ELECTROCARDIOGRAM NOT DONE
- 6.06 3 MONTHS - ELECTROCARDIOGRAM NOT DONE WITHIN FOLLOW-UP WINDOW
- 6.07 3 MONTHS - ECHOCARDIOGRAM NOT DONE
- 6.08 3 MONTHS - ECHOCARDIOGRAM NOT DONE WITHIN FOLLOW-UP WINDOW
- 6.09 3 MONTHS - BLOOD NOT DONE
- 6.10 3 MONTHS - BLOOD INCOMPLETE
- 6.11 3 MONTHS - COAGULATION PROFILE NOT DONE (ONLY REQUIRED FOR PATIENTS ON ANTICOAGULANT THERAPY)
- 6.12 3 MONTHS - BLOOD NOT DONE WITHIN FOLLOW-UP WINDOW
- 6.13 3 MONTHS - MEDICATIONS NOT ASSESSED
- 6.14 3 MONTHS - MEDICATIONS NOT ASSESSED WITHIN FOLLOW-UP WINDOW
- 6.15 3 MONTHS - OTHER DEVIATION

CONFIDENTIAL AND PROPRIETARY DATA: This document and the information contained herein may not be reproduced, used, or disclosed without written permission from Edwards Lifesciences LLC

1-YEAR

8.01 1 YEAR - SUBJECT NOT CONTACTED
8.02 1 YEAR - ASSESSMENT NOT DONE WITHIN FOLLOW-UP WINDOW
8.03 1 YEAR - PHYSICAL ASSESSMENT / VITAL SIGNS NOT DONE
8.04 1 YEAR - NYHA NOT DONE
8.05 1 YEAR - ELECTROCARDIOGRAM NOT DONE
8.06 1 YEAR - ELECTROCARDIOGRAM NOT DONE WITHIN FOLLOW-UP WINDOW
8.07 1 YEAR - ECHOCARDIOGRAM NOT DONE
8.08 1 YEAR - ECHOCARDIOGRAM NOT DONE WITHIN FOLLOW-UP WINDOW
8.09 1 YEAR - BLOOD NOT DONE
8.10 1 YEAR - BLOOD INCOMPLETE
8.11 1 YEAR - COAGULATION PROFILE NOT DONE (ONLY REQUIRED FOR PATIENTS ON ANTICOAGULANT THERAPY)
8.12 1 YEAR - BLOOD NOT DONE WITHIN FOLLOW-UP WINDOW
8.13 1 YEAR - MEDICATIONS NOT ASSESSED
8.14 1 YEAR - MEDICATIONS NOT ASSESSED WITHIN FOLLOW-UP WINDOW
8.15 1 YEAR - EQ-5D NOT DONE
8.16 1 YEAR - SF-12 NOT DONE
8.17 1 YEAR - OTHER DEVIATION

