3 YEAR

10.01 3 YEAR - SUBJECT NOT CONTACTED
10.02 3 YEAR - ASSESSMENT NOT DONE WITHIN FOLLOW-UP WINDOW
10.03 3 YEAR - PHYSICAL ASSESSMENT / VITAL SIGNS NOT DONE
10.04 3 YEAR - NYHA NOT DONE
10.05 3 YEAR - ELECTROCARDIOGRAM NOT DONE
10.06 3 YEAR - ELECTROCARDIOGRAM NOT DONE WITHIN FOLLOW-UP WINDOW
10.07 3 YEAR - ECHOCARDIOGRAM NOT DONE
10.08 3 YEAR - ECHOCARDIOGRAM NOT DONE WITHIN FOLLOW-UP WINDOW
10.09 3 YEAR - BLOOD NOT DONE
10.10 3 YEAR - BLOOD INCOMPLETE
10.11 3 YEAR - COAGULATION PROFILE NOT DONE (ONLY REQUIRED FOR PATIENTS ON ANTICOAGULANT THERAPY)
10.12 3 YEAR - BLOOD NOT DONE WITHIN FOLLOW-UP WINDOW
10.13 3 YEAR - MEDICATIONS NOT ASSESSED
10.14 3 YEAR - MEDICATIONS NOT ASSESSED WITHIN FOLLOW-UP WINDOW
10.15 3 YEAR - OTHER DEVIATION

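### The schedule and the deviation codes disagree on who has follow-up coagulation tests, so the section 9.5 summary can depend on which rule a site followed

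*Combined protocol and SAP*

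**What the plan says.** **Schedule.** Section 7.3.3 reads "Coagulation profile will be collected at baseline, discharge, 3 months, and at the 1, 3, and 5 year follow-up visits". Table 3 marks the same time points. Neither makes the test conditional on treatment. Section 10.4.3 applies follow-up to everyone: "Post-procedure clinical evaluation will be performed on all enrolled trial subjects at scheduled visits at the trial site".

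**Table 8.** This table covers all post-discharge visits, including 3 months. Its footnote 2 says "Coagulation profile will be completed only at years 1, 3, and 5". That sets no anticoagulant condition, but it leaves out 3 months.

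**Deviation codes (Appendix 15.4).** Code 6.11 reads "3 MONTHS - COAGULATION PROFILE NOT DONE (ONLY REQUIRED FOR PATIENTS ON ANTICOAGULANT THERAPY)", code 8.11 "1 YEAR - COAGULATION PROFILE NOT DONE (ONLY REQUIRED FOR PATIENTS ON ANTICOAGULANT THERAPY)" and code 10.11 "3 YEAR - COAGULATION PROFILE NOT DONE (ONLY REQUIRED FOR PATIENTS ON ANTICOAGULANT THERAPY)". Code 12.11 carries the same restriction at 5 years. The baseline code (2.06) and the discharge code (4.05) have no such restriction.

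**Analysis.** Section 9.5 is one sentence: "The mean and standard deviation of blood data will be calculated and presented". Section 9.6 uses available valid data with no imputation. Coagulation falls under blood data: it is described in 7.3.3, listed under blood tests in Table 3 and recorded on the Blood Data form.

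**Treatment over time.** Section 10.4.1 leaves anticoagulation to the investigator's discretion, for roughly the first 2 to 3 months. It continues "Anticoagulants should then be discontinued over a period of 10 days", and then excepts patients with an ongoing indication.

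**The concern.** For a subject who is off anticoagulants at a follow-up visit, the documents give opposite answers. Under 7.3.3 and Table 3 the test is due, and section 12.6 would make its omission a deviation. Under the code label the test is not required, and its omission is not a coagulation deviation. With up to six sites, some may test everyone and others only treated subjects, and the deviation log would not show the difference.

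The baseline and discharge codes are unrestricted, so the tested group could change between discharge and 3 months, at about the time section 10.4.1 describes anticoagulation being withdrawn. A series of visit means could then show INR holding up or rising only because untreated subjects had dropped out of the denominator. At stake is whether the follow-up INR/PTT table can be read at all.

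**Working it through.** The plan states no INR or PTT value and no share of subjects expected to be on treatment, so there is no figure to reproduce. The check has two parts.

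**1. The passages side by side**

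| Visit | 7.3.3 and Table 3 | Table 8, footnote 2 | Deviation code |
|---|---|---|---|
| Baseline | all subjects | not covered | 2.06: no restriction |
| Discharge | all subjects | not covered | 4.05: no restriction |
| 3 months | all subjects | not done | 6.11: anticoagulated only |
| 1 year | all subjects | done, no condition | 8.11: anticoagulated only |
| 3 years | all subjects | done, no condition | 10.11: anticoagulated only |
| 5 years | all subjects | done, no condition | 12.11: anticoagulated only |

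The restriction appears at every follow-up visit where the test is scheduled and at neither earlier time point, so it does not look like an isolated slip. At 3 months the three sources give three different answers.

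**2. How far the visit mean could move**

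Inputs:
- *p*, the share of attending subjects on anticoagulants: assumed, 15% to 90%.
- *q*, the share of subjects off anticoagulants who are still tested: 1 if sites follow the schedule, 0 if they follow the codes, 0.5 for a mixture.
- Mean INR of 2.5 on treatment and 1.1 off: assumed, not in the documents.
- 200 subjects at the visit: the enrolment ceiling in section 9.1, ignoring attrition.

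The treated share among those tested is w = p / (p + (1 − p)q). The reported mean is 2.5w + 1.1(1 − w).

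Example with p = 0.30:
- q = 1: w = 0.30, mean = 0.75 + 0.77 = 1.52, n = 200.
- q = 0.5: w = 0.30 / 0.65 = 0.4615, mean = 1.75, n = 130.
- q = 0: w = 1, mean = 2.50, n = 60.

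| p | All tested (q = 1) | Half of untreated tested (q = 0.5) | Treated only (q = 0) | Gap, q = 0 minus q = 1 |
|---|---|---|---|---|
| 90% | 2.36 (n = 200) | 2.43 (n = 190) | 2.50 (n = 180) | 0.14 |
| 60% | 1.94 (n = 200) | 2.15 (n = 160) | 2.50 (n = 120) | 0.56 |
| 30% | 1.52 (n = 200) | 1.75 (n = 130) | 2.50 (n = 60) | 0.98 |
| 15% | 1.31 (n = 200) | 1.47 (n = 115) | 2.50 (n = 30) | 1.19 |

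The full gap is (1 − p) × (2.5 − 1.1) = 1.4(1 − p), so it grows as fewer subjects remain on treatment. With half of the untreated subjects tested, the departure from the all-tested mean is smaller: 0.07, 0.21, 0.23 and 0.16 for the four rows. The shift is upward whenever INR is higher on treatment than off. PTT was not quantified.

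**The case against.** The best counter-argument is that deviation codes only classify what gets reported, while Table 3 tells sites what to do. A test that is not a deviation when missed may still be done. Section 12.6.1 also accepts that some non-essential data may be absent without a deviation. This lowers the likelihood of the problem but does not remove the conflict. Section 12.6.1 does not name coagulation, the four codes say in terms for whom the test is required, and no rule puts the body of the protocol above the appendices. The general codes for incomplete blood work (such as 6.10) do not mention coagulation either.

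Some stronger readings are tempting, but the documents do not support them:

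- *Section 9.5 prescribes one pooled mean.* It does not say so. It is silent on splitting, on denominators and on visits, and pooling is an inference from that silence.
- *Later values would describe only an anticoagulated minority.* No proportion is given. Section 10.4.1 is discretionary and lists several reasons to continue. The 3-month window of ± 1 month means some subjects may still be on treatment or tapering at that visit.
- *These are the only data for interpreting bleeding and thromboembolism.* They are the only scheduled coagulation laboratory results. However, Appendix 15.1 asks for anticoagulant or antiplatelet use with each reported bleed, the Adverse Event form asks whether antithrombotic medication contributed, and medications are recorded at baseline, discharge and every follow-up visit.
- *Table 8 supports testing at 3 months.* Its footnote says the reverse.

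It is also fair to say that a split by treatment is a presentation choice in a descriptive study. That bears on the weight of the point, not on whether it is true.

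**Conclusion.** The point holds as an inconsistency with a limited analytic consequence. The schedule and the codes contradict each other on who is tested at 3 months and years 1, 3 and 5. The Table 8 footnote also contradicts the schedule on whether 3 months is tested at all. Nothing in the documents resolves either conflict.

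Because 9.5 has no split by anticoagulant use and 9.6 takes the data as they come, the follow-up INR/PTT summary can depend on site practice. Under the assumed INR values the dependence runs from about 0.14 (90% treated) to about 1.19 (15% treated). Those figures are the extreme comparison of every site testing all subjects against every site testing only treated subjects, and mixed practice gives less.

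A reader might infer that the safety results are affected. They are not: coagulation is Other Data, section 9 makes no endpoint depend on it, and no endpoint estimate changes.

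**What to change.** 1. Reconcile 7.3.3, Table 3, footnote 2 of Table 8 and codes 6.11, 8.11, 10.11 and 12.11, so that all state the same rule on who is tested and at which visits. The choice of rule is the sponsor's.
2. In section 9.5, report coagulation as N, mean and SD at each visit, separately for subjects on and off anticoagulants. Classify subjects from the Medications form completed at the same visit, and give the number tested out of the number attending.

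With the split, each group's mean no longer depends on the testing rule, provided testing within the group is unselective. It does not recover untested subjects: if only treated subjects are tested, the off-treatment row will be empty or sparse, and the table will show that openly.

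The cost is an aligned footnote and four code labels, any matching edit to the schedule, and a sentence or two in 9.5. The split needs no new data, since medications are already scheduled at baseline, discharge and every follow-up visit. The downside is a smaller N per cell.

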8 SUBJECT POPULATION

8.1 DEMOGRAPHIC AND CLINICAL CHARACTERISTICS

Adult subjects diagnosed with aortic valve disease and scheduled to undergo aortic valve replacement are eligible for participation in the clinical trial.

8.2 INCLUSION CRITERIA

The principal investigator at the trial site has the responsibility of screening potential subjects to determine if the patients meet all the inclusion criteria. The following are requirements for entry into the clinical trial:

- Is 18 years or older
- Provides written informed consent prior to trial procedures
- Diagnosed with aortic valve disease requiring a planned replacement as indicated in the preoperative evaluation
- Scheduled to undergo planned aortic valve replacement with or without concomitant bypass surgery
- Geographically stable and agrees to attend all follow-up assessments at the hospital of surgical services for up to 5 years

8.3 EXCLUSION CRITERIA

The principal investigator at the trial site must exclude subjects if any of the exclusion criteria are present. The following are the criteria for exclusion from participating in the clinical trial:

- Requires emergency surgery³
- Has prior mitral, tricuspid or pulmonic valve surgery, which included implant of a bioprosthetic valve, mechanical valve, or annuloplasty ring that will remain *in situ*
- Requires multiple valve replacement/repair
- Requires a surgical procedure outside of the cardiac area (e.g. vascular bypass)
- Has aneurysm of the aortic root and/or ascending aorta requiring surgical intervention
- Has active endocarditis/myocarditis or endocarditis/myocarditis within 3 months to the scheduled aortic valve replacement (AVR) surgery
- Has renal insufficiency as determined by creatinine (S-Cr) level ≥ 2.5 mg/dL or end-stage renal disease requiring chronic dialysis at screening visit
- Has MRI or CT scan confirmed stroke, cerebrovascular accident (CVA) or transient ischemic attack (TIA) within 6 months (180 days) prior to AVR surgery
- Has acute myocardial infarction (MI) within 30 days prior to AVR surgery
- Has presence of non-cardiac disease limiting life expectancy to less than 12 months
- Diagnosed with hypertrophic obstructive cardiomyopathy (HOCM)
- Diagnosed with hyperparathyroidism
- Exhibits left ventricular ejection fraction $\leq 30\%$ as validated by diagnostic procedure within 30 days prior to AVR surgery
- Echocardiographic evidence of an intra-cardiac mass, thrombus, or vegetation
- Hemodynamic or respiratory instability requiring inotropic support, mechanical circulatory support, or mechanical ventilation within 60 days prior to AVR surgery

³ Emergent surgery – surgery is carried out on the referral day before the beginning of the next working day.

- Documented leukopenia ($WBC < 3.5 \times 10^3/\mu L$), acute anemia ($Hgb < 10.0 \text{ gm/dL}$ or 6 mmol/L), thrombocytopenia (platelet count $< 50 \times 10^3/\mu L$) or history of bleeding diathesis or coagulopathy
- Diagnosed with myxomatous disease/connective tissue disorders (e.g. Marfan's Syndrome)
- Has prior organ transplant
- Current or recent participation (within 6 weeks prior to surgery) in an investigational drug or device trial
- Was previously implanted with trial device⁴
- Pregnant (female subject of childbearing potential only), lactating or planning to become pregnant during the duration of participation in trial
- Currently incarcerated or unable to give voluntary informed consent
- Documented history of substance (drug or alcohol) abuse within the last 5 years prior to implant

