	
Exclusion Criteria
 
 • Requires emergency surgery¹ • Has prior mitral, tricuspid or pulmonic valve surgery, which included implant of a bioprosthetic valve, mechanical valve, or annuloplasty ring that will remain in situ • Requires multiple valve replacement/repair • Requires a surgical procedure outside of the cardiac area (e.g. vascular bypass) • Has aneurysm of the aortic root and/or ascending aorta requiring surgical intervention • Has active endocarditis/myocarditis or endocarditis/myocarditis within 3 months to the scheduled aortic valve replacement (AVR) surgery • Has renal insufficiency as determined by creatinine (S-Cr) level ≥ 2.5 mg/dL or end-stage renal disease requiring chronic dialysis at screening visit • Has MRI or CT scan confirmed stroke, cerebrovascular accident (CVA) or transient ischemic attack (TIA) within 6 months (180 days) prior to AVR surgery • Has acute myocardial infarction (MI) within 30 days prior to AVR surgery • Has presence of non-cardiac disease limiting life expectancy to less than 12 months • Diagnosed with hypertrophic obstructive cardiomyopathy (HOCM) • Diagnosed with hyperparathyroidism • Exhibits left ventricular ejection fraction $\leq 30\%$ as validated by diagnostic procedure within 30 days prior to AVR surgery • Echocardiographic evidence of an intra-cardiac mass, thrombus, or vegetation • Hemodynamic or respiratory instability requiring inotropic support, mechanical circulatory support, or mechanical ventilation within 60 days prior to AVR surgery • Documented leukopenia ($WBC < 3.5 \times 10^3/\mu L$), acute anemia ($Hgb < 10.0$ gm/dL or 6 mmol/L), thrombocytopenia (platelet count $< 50 \times 10^3/\mu L$) or history of bleeding diathesis or coagulopathy • Diagnosed with myxomatous disease/connective tissue disorders (e.g. Marfan's Syndrome) • Has prior organ transplant • Current or recent participation (within 6 weeks prior to surgery) in an investigational drug or device trial • Was previously implanted with trial device²
--	--

¹ Emergent surgery – surgery is carried out on the referral day before the beginning of the next working day.

² Note: Previously implanted means that the index aortic valve replacement procedure was completed. The procedure is complete when the surgeon takes the subject off cardiopulmonary bypass and restarts the heart.

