12.6 PROTOCOL DEVIATIONS

A protocol deviation is defined as an event where the Investigator or trial personnel did not conduct the trial according to the clinical protocol or the Clinical Trial Agreement.

Deviations shall be reported to the Trial Sponsor regardless of whether medically justifiable or taken to protect the subject in an emergency. Subject specific deviations and non-subject specific deviations, (e.g. unauthorized use of a trial device outside the trial, unauthorized use of a trial device by a physician who is not listed in the Clinical Trial Agreement, etc.) will be reported in writing. Investigators will also adhere to procedures for reporting trial deviations to their EC in accordance with their specific EC's reporting policies and procedures.

For reporting purposes, deviations are classified as major or minor:

- Major deviations:
 - Any deviation from subject inclusion and exclusion criteria;
 - Any deviation from subject informed consent procedures;
 - Unauthorized use of an trial device outside the trial;
 - Unauthorized use of a trial device by a physician who is not listed in the Clinical Trial Agreement.
- Minor deviations:
 - Deviation from a protocol requirement such as incomplete/inadequate testing procedures;
 - Follow-up performed outside specified time windows.

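### The hemoglobin exclusion limit pairs 10.0 g/dL with 6 mmol/L, which are not equivalent: a minor inconsistency that takes effect only if a laboratory reports mmol/L

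*Combined protocol and SAP*

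**What the plan says.** Section 8.3 (Exclusion Criteria) lists, within its blood-count criterion, "acute anemia ($Hgb < 10.0 \text{ gm/dL}$ or 6 mmol/L". The Protocol Synopsis gives the same pair: "acute anemia ($Hgb < 10.0$ gm/dL or 6 mmol/L". Item 16 of the preoperative inclusion/exclusion form in Appendix 15.3 repeats it as a yes/no question, so the answer does not show which unit was used. None of the three places gives a conversion factor, a rounding rule or a governing unit.

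The criterion is binding. Section 8.3 says that the principal investigator "must exclude subjects if any of the exclusion criteria are present". Section 12.6 puts first among its major deviations "Any deviation from subject inclusion and exclusion criteria", and Appendix 15.4 has a separate code, 1.02, for a subject who met an exclusion criterion.

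**The concern.** Two units in one criterion help only if they mark the same point. Here one figure has a decimal and the other is a whole number, and on the usual conversion they do not meet. The gap runs one way: a value inside it is excluded by the g/dL figure and passes the mmol/L figure.

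What is at stake is consistent eligibility. For the same blood value, a site working in g/dL would exclude the candidate, or be recorded under code 1.02 with a major deviation if it enrolled them. A site comparing a mmol/L report with 6 would enroll the same candidate and see nothing to report. The error appears identically in all three places, so no other part of the document corrects it.

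**Working it through.** **Inputs.** From the protocol (synopsis, Section 8.3, CRF item 16): 10.0 g/dL and 6 mmol/L. From outside the protocol, as an assumption: the hemoglobin monomer, molar mass M of about 16,114 g/mol, the usual basis for reporting hemoglobin in mmol/L. M from 16,000 to 16,125 was also tried.

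**Formula.** mmol/L = (g/dL × 10 / M) × 1000.

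**Can the plan's own pairing be reproduced?** For 10.0 g/dL to equal 6 mmol/L, M must be 10.0 × 10 × 1000 / 6 = 16,667 g/mol, a factor of 0.600. That lies outside the range tried for the monomer. The tetramer (M about 64,458) gives 10.0 g/dL = 1.55 mmol/L, so it does not reconcile the figures either.

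**Conversion on the monomer basis.**

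| Factor (mmol/L per g/dL) | 10.0 g/dL in mmol/L | 6 mmol/L in g/dL |
|---|---|---|
| 0.620 | 6.20 | 9.68 |
| 0.6206 | 6.21 | 9.67 |
| 0.625 | 6.25 | 9.60 |

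At 0.6206 the gap is 10.0 − 9.67 = 0.33 g/dL, or about 0.2 mmol/L.

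**Individual values at 0.6206.**

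| g/dL | mmol/L | Below 10.0 g/dL? | Below 6 mmol/L? |
|---|---|---|---|
| 9.6 | 5.96 | yes | yes |
| 9.7 | 6.02 | yes | no |
| 9.8 | 6.08 | yes | no |
| 9.9 | 6.14 | yes | no |
| 10.0 | 6.21 | no | no |

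The limits disagree only from about 9.67 to just under 10.0 g/dL.

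**How many candidates lie there?** The protocol gives no hemoglobin distribution. Assume a normal distribution with mean 12.5 to 13.5 and SD 1.5 to 1.7 g/dL, and take P(Hgb < 10.0) − P(Hgb < 9.67). The two extremes are:

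- Mean 13.5, SD 1.5: 0.98% − 0.53% = 0.45%, or 0.9 per 200 candidates, out of 2.0 per 200 below 10.0 g/dL.
- Mean 12.5, SD 1.7: 7.07% − 4.79% = 2.28%, or 4.6 per 200 candidates, out of 14.1 per 200 below 10.0 g/dL.

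With the factor 0.625 the band starts at 9.60 g/dL and the upper figure becomes 7.07% − 4.40% = 2.67%, or 5.3 per 200. The order of magnitude does not change.

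These counts are candidates in the band, not candidates misclassified. The two are equal only if every laboratory reports mmol/L and every site ignores the g/dL figure. The count also treats any value below 10.0 g/dL as meeting the criterion, although the criterion speaks of documented, acute anemia.

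**The case against.** The strongest reply is that the wording contains no conflict. The limits are joined by *or*, and any criterion that is met excludes. Every value below 6 mmol/L is already below 10.0 g/dL, so the g/dL limit governs and a candidate at 9.8 g/dL is excluded whatever unit is printed. That is the literal reading, and it reduces the problem. It also leaves the mmol/L figure with no function. Its only sensible purpose is to serve a laboratory that reports mmol/L, and staff holding such a report would compare with 6 rather than convert back.

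The second reply is that 6 is simply 6.2 written as a whole number. That is probably how it arose, and it explains why the gap is small. It does not make the two limits equal.

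The third reply stands. A reader might infer that entry rules do differ between the sites. The documents do not support this, because they nowhere say that any laboratory reports hemoglobin in mmol/L. The Blood Data form shows no unit beside hemoglobin. Other laboratory limits use mass units only: creatinine in mg/dL in Section 8.3 and on the Demographics form, and plasma free hemoglobin in mg/dL in the adverse event definitions. Printing both units suggests that the sponsor expected mmol/L somewhere, but it does not show it. If no laboratory uses mmol/L, nobody is affected.

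A reader might also infer that the bleeding or hemolysis results are put at risk. That is not supported either. The safety endpoints are descriptive (Section 7.3.1), the trial has no comparison group, Section 9 sets no hypothesis test, and the Appendix 15.1 definitions of bleeding and hemolysis do not use this entry limit.

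**Conclusion.** The point holds as a minor inconsistency. A mandatory entry limit is stated as two values that differ by about 0.33 g/dL (0.2 mmol/L), and nothing in the document reconciles them. The inequality rests on the monomer conversion, which comes from outside the protocol, but it holds at every monomer mass tried.

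The practical effect is conditional. It needs a laboratory that reports mmol/L, a site that compares with 6 alone, and a candidate between about 9.67 and just under 10.0 g/dL. Under the assumed distributions about 0.45% to 2.3% of candidates, or about 1 to 5 per 200, lie in that band. This is an upper bound on those affected, and the true number may be zero. What can change is who is eligible at the margin and whether code 1.02 is raised for a given value. The sample size statement and the planned descriptive analyses are unaffected. Which of the two limits is clinically right is not judged here.

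**What to change.** Reconcile the pair in the synopsis, Section 8.3 and CRF item 16 in one of two ways:

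- state the sponsor's intended limit with its equivalent to one decimal in both units (as conversions only, 10.0 g/dL pairs with 6.2 mmol/L, and 6.0 mmol/L pairs with 9.7 g/dL); or
- keep both figures and state which unit governs and how the other is converted.

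Then check the baseline hemoglobin of subjects already enrolled under this wording against the stated limit. The value is collected at baseline (Sections 7.3.3 and 10.1.3), so no new data are needed. Section 5.2.3 reports twenty subjects implanted under Version A; the wording that applied to them is not in these documents and should be confirmed before they are included in the check.

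The cost is one figure or one sentence in three places, plus a data query. The only drawback is that a few additional deviations may have to be listed.
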